1 INTRODUCTION

CooperVision's Proclear material (omafilcon A) has been longstanding, successful hydrogel lens material available in a daily disposable modality. The popularity of silicone hydrogels materials in a daily disposable modality has increased over time, offering superior oxygen delivery to the eye and the convenience of single-use lenses. One recent publication has found no clinically significant physiological differences in five retrospective studies where patients were refit from a range of hydrogel lenses to silicone hydrogel lenses.¹

This aim of this study is to determine if habitual or adapted contact lens wearers of Proclear 1 Day (omafilcon A) can be confidently refit into Clariti 1 Day (somofilcon A) lenses and be successful after one week of daily wear. The primary target population for this study will ideally be habitual wearers of Proclear 1 Day. However, as a secondary target population, habitual wearers of other lens types will be recruited and will be adapted to Proclear 1 Day lenses for at least 7 days before being refit into Clariti 1 Day.

2 OBJECTIVES

The objective of the study is to determine if habitual or adapted contact lens wearers of Proclear 1 Day can be confidently refit into Clariti 1 Day (somofilcon A) lenses and be successful after one week of daily wear.

The primary outcome variables for this study are:

- Investigator responses to refit questions;
- Lens fit.

[REDACTED]

[REDACTED]

3 HYPOTHESIS

The null hypothesis for this study is that there is no difference in lens fit performance between Proclear 1 Day (omafilcon A) and Clariti 1 Day (somofilcon A) lenses.

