4.5.5 STUDY LENS OPTIMIZED FITTING (PROCLEAR 1 DAY AND CLARITI 1 DAY)

The overall fit of Proclear 1 Day (habitual or new fitting) and Clariti 1 Day will be assessed for the following, after at least 2 minutes settling time:

- Lens wettability (0-4, 0.25 steps, where 0 = excellent, 4 = very poor)
- Lens deposition (0-4, 0.5 steps, where 0 = no deposits, 4 = deposits \geq 0.5mm or film > 75% of surface)
- Decentration (optimum / decentration acceptable / decentration unacceptable)
- Corneal coverage in primary gaze (yes / no)
- Post-blink movement (0-4, 1 step, where 0 = insufficient, unacceptable movement, 2=optimal movement, 4=excessive, unacceptable movement)
- Tightness on push-up (0-100%, 5% steps, where 0% = falls from the cornea, 50% = optimum, 100% = no movement)
- Overall fit acceptance (0-4, 1 step, where 0 = should not be worn, 4 = perfect), providing a reason if Grade 2 or less

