4.5.6 STUDY LENS FIT ASSESSMENT

The study lenses will be assessed for the following during the lens fit assessment at Visit 1B and Visit 3:

- Lens wettability (0-4, 0.25 steps, where 0 = excellent, 4 = very poor)
- Lens deposition (0-4, 0.5 steps, where 0 = no deposits, 4 = deposits \geq 0.5mm or film > 75% of surface)

- Decentration (optimum / decentration acceptable / decentration unacceptable)
- Corneal coverage in primary gaze (yes / no)
- Post-blink movement (0-4, 1 step, where 0 = insufficient, unacceptable movement, 2 = optimal movement, 4 = excessive, unacceptable movement)
- Tightness on push-up (0-100%, 1% steps, where 0% = falls from the cornea, 50% = optimum, 100% = no movement)
- Overall fit acceptance (0-4, 1 step, where 0 = should not be worn, 4 = perfect), providing a reason if Grade 2 or less

[Redacted]

[Redacted]

[Redacted]

[Redacted]

[Redacted]

[Redacted]

[Redacted]

[Redacted]

[REDACTED]

[REDACTED]

[REDACTED]

[REDACTED]

[REDACTED]

[REDACTED]

[REDACTED]

[REDACTED]

[REDACTED]

[REDACTED]

[REDACTED]

[REDACTED]

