11 STATISTICAL ANALYSIS AND DATA MANAGEMENT

11.1 STATISTICAL ANALYSIS

All data will be analyzed by the CCLR at the University of Waterloo. Unmasked data analysis will be conducted using Statistica 12 and/or SPSS 24. Descriptive statistics will be provided on information regarding baseline variables (age, gender, refractive error distribution, etc.). For data completed on each eye individually (e.g. biomicroscopy), results of the right eye will be reported unless a difference between right eye and left eye is found. Table 4 lists the primary outcome variables and anticipated statistical procedures.

Table 4 : Statistical procedures

Variable	Analysis	Statistical test
Numeric rating scales Visual acuity Lens fitting Biomicroscopy (continuous variables)	Effect of lens type	Paired t-test Wilcoxon matched pairs test
Biomicroscopy (ordinal variables)	Effect of lens type	Friedman Wilcoxon matched pairs test
Subjective preference ratings Investigator refit agreement ratings	Preference of lens type	Binomial test

All data will be tested for normality of distribution using Shapiro-Wilk tests. The appropriate statistical test will be selected based on tests of normality. Statistical significance will be set at 5%, with no adjustments for multiple comparisons. In the event of missing data, individual data points will be excluded in the analysis and not extrapolated from the collected data.

A binomial test will be used to analyze the results for the count data of subjective preferences and investigator refit agreement ratings. The number of “no preference” (if featured on the scale) will be evenly distributed to the two options on the basis respondents would be equally likely to choose either.

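### The lens-fit null hypothesis rests on seven items at several visits, with no deciding item, visit pair or rejection rule named

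*Combined protocol and SAP*

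**What the plan says.** Section 2 introduces two outcomes with "The primary outcome variables for this study are": investigator refit responses and lens fit. No item, score or visit is attached to the second. Section 3 gives the only hypothesis, that "there is no difference in lens fit performance" between the Proclear and Clariti lenses.

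Section 4.5.6 defines the measurement: "The study lenses will be assessed for the following during the lens fit assessment at Visit 1B and Visit 3". Seven items follow: wettability, deposition, decentration (three categories), corneal coverage (yes/no), post-blink movement, push-up tightness and, last, "Overall fit acceptance (0-4, 1 step, where 0 = should not be worn, 4 = perfect". The last item has no special status. Table 3 schedules the fit assessment at Visits 1, 1A, 1B, 2 and 3.

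Table 4 in section 11.1 has one entry for lens fitting, analysed for the effect of lens type by paired t-test or Wilcoxon matched pairs test. The section then states: "Statistical significance will be set at 5%, with no adjustments for multiple comparisons". Neither participants nor investigators are masked (section 4.1.3), and the analysis is unmasked (section 11.1).

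**The concern.** A single null needs a single way of being rejected. Here seven results, from several possible pairs of visits, could each be held up as the answer. The items can disagree: the lenses differ in material and water content (Table 1), so wettability or deposits could change while the overall fit grade does not. Under the plan as written, that could be reported as a difference in lens fit performance. An unmasked team could also settle which item counts after seeing the data. At stake is the 5% error rate that the plan claims for its only stated hypothesis, and what a rejection would mean.

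**Working it through.** **The plan's own figure.** The plan gives no error rate or power for lens fit. Its only design calculation (section 4.2.1) is for comfort: 67 participants, alpha 0.05, power 0.8, difference 7 on a 0-100 scale. No SD is given, so 67 cannot be reproduced. Solving the two-sided paired formula backwards gives an implied SD of differences of 7 × √67 / (1.960 + 0.842) ≈ 20.5. That figure concerns comfort only. The 67 enters below only in step 4.

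**Step 1: look for a decision rule.**

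| Place | What it fixes | What it leaves open |
|---|---|---|
| Section 2 | Lens fit is primary | Item, visit |
| Section 3 | One null on lens fit performance | Item, visit, rejection rule |
| Section 4.5.6 | Seven items; Visits 1B and 3 | Which item decides |
| Table 3 | Fit assessed at five visits | Which visits are paired |
| Section 11.1, Table 4 | Paired univariate tests at 5%, no adjustment | Item, visit pair, composite or hierarchy |

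No readable place closes the gap.

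**Step 2: how many tests.** The tests named are univariate and no composite is defined. The items also share no common scale: the best value is 0 for wettability and deposition, 2 for movement, 50% for tightness and 4 for overall acceptance. Separate testing is therefore the natural reading. Seven items is the full list. Five is a reasonable lower count, either because decentration and coverage are not numeric and may hardly vary, or because the two surface ratings are set aside.

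**Step 3: chance of at least one false positive**, if any significant item is taken to reject the null. For k independent tests at 5% it is 1 − 0.95^k:
- k = 7: 1 − 0.95^7 = 0.302
- k = 5: 1 − 0.95^5 = 0.226

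For correlated items, 300,000 simulated sets of two-sided z-tests with an assumed common correlation r give:

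| r (assumed) | 7 items | 5 items |
|---|---|---|
| 0 | 0.30 | 0.23 |
| 0.3 | 0.27 | 0.21 |
| 0.5 | 0.23 | 0.18 |
| 0.8 | 0.15 | 0.13 |

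**Step 4: a real difference on one item only.** Suppose wettability truly differs and nothing else does. With 67 pairs and a two-sided paired t-test, wettability alone is significant with probability about 0.37, 0.81 or 0.98 if the true difference is 0.2, 0.35 or 0.5 SD of the paired differences. These effect sizes are assumptions, as the documents give none.

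**Step 5: after a change.** With one deciding item, the error rate for this null is 0.05. Keeping all seven with Bonferroni means testing each at 0.05/7 = 0.00714, which gives 0.049 if independent. Removing only the two surface ratings leaves 0.226 if independent, so removal alone does not solve the problem.

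**The case against.** The best defence has four parts.

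- Table 4 has one lens fitting entry and does not say that seven tests will be run. This stands: separate testing is an inference, though no composite is offered in its place.
- The 30% figure needs seven independent, fully varying items. This also stands. Inclusion criterion 6 requires an acceptable fit with both lenses, so coverage and decentration may hardly vary, and the other items are probably correlated. The figure is an upper one.
- The protocol may define lens fit as it likes, and it lists wettability and deposition under the fit assessment. Accepted: the point does not depend on calling them something else.
- Section 4.5.6 names Visits 1B and 3, which suggests the intended comparison. It does suggest it, but section 11.1 does not adopt it and Table 3 offers other visits.

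Parts of sections 2 and 4.5.6 are blacked out. The primary outcomes, the null, the seven items and the analysis section are readable, and none names a deciding item.

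Three stronger readings are tempting, and the documents do not support them.

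- A reader might infer that the plan prescribes rejection on any one item. It gives no rule at all, so such rejection is permitted, not prescribed.
- A reader might infer that a real change in overall fit would be diluted by the other six items. Separate unadjusted tests take no power from one another. Dilution would need a composite or an adjustment, and the plan has neither.
- A reader might see "Tightness on push-up (0-100%, 5% steps" in section 4.5.5 beside "Tightness on push-up (0-100%, 1% steps" in section 4.5.6 and infer that baseline tightness is recorded more coarsely than follow-up, because Visit 1B can fall within Visit 1. The 5% steps belong to the optimized fitting. Section 4.5.6 applies 1% steps explicitly to both Visit 1B and Visit 3, and section 4.4.1.1 has Visit 1B completed as its own assessment even when it is concurrent.

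**Conclusion.** The concern holds as an unspecified primary comparison: no item, visit pair or decision rule is tied to the only null hypothesis. If items are tested separately and any significant one may be cited, the false-positive chance is at most about 30%, about 23% for five independent items, and about 13% to 18% for five items at correlations of 0.8 to 0.5. These figures assume two-sided tests (sidedness is not stated) and assumed correlations. The exact value cannot be known from the documents, but every case examined exceeds 5%. The gap also lets a change in wettability or deposits alone be presented as a rejection of the lens-fit null. It does not show that the study would do so.

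**What to change.** In sections 2, 3 and 11.1, name overall fit acceptance (0-4), Clariti at Visit 3 against Proclear at Visit 1B, as the single measure on which the lens-fit null is judged, using the Wilcoxon matched pairs test already in Table 4. State that the other six items, including wettability and deposition, are supporting results that do not decide the null.

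This is a change of wording on data already collected, and it restores a 5% error rate for this null. It does not address the other primary outcome, the investigator refit responses.

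There are two costs. Differences on single items can no longer be claimed as the primary result. And the five-grade scale may cluster at high grades, because acceptable fit is required at entry. With many tied pairs the test has little to work on: an exact two-sided test cannot reach 5% unless at least six participants change grade (2 × 0.5^5 = 0.0625; 2 × 0.5^6 = 0.031). The documents give no SD or power for this item, so a non-significant result should not be read as showing equal fit.

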4 MATERIALS AND METHODS

4.1 STUDY DESIGN

4.1.1 OVERALL DESIGN

This is a prospective, single-site, dispensing, bilateral wear, open label, daily wear switch study, with the test lens (Clariti 1 Day) being worn for 7 (+5) days.

Participants will attend a screening visit (Visit 1), at which consent will be obtained and eligibility to participate will be confirmed. The number of visits is dependent the participant's habitual lens type (i.e. whether it is Proclear 1 Day, or another lens type) and whether the power of the habitual lens needs to be changed. All subjects will be fit with Clariti 1 Day at the screening visit to ensure they can successfully wear the product.

Habitual wearers of Proclear 1 Day lenses will be reviewed at Visit 1 to ensure optimal visual acuity is being achieved. If the visual acuity and power of the habitual Proclear 1 Day lens is optimal, participants will be fit with Clariti 1 Day and asked to return for evaluation after 7 days of lens wear.

If an amendment of the power of the habitual Proclear 1 Day is required, participants will be dispensed with the new power of the Proclear 1 Day lenses to be worn for at least 7 days. Participants will return after wearing the Proclear 1 Day lenses to collect baseline variables. The participant will then be dispensed with Clariti 1 Day and asked to return for evaluation after 7 days of lens wear.

In the instance where the participant habitually wears lenses which are not Proclear 1 Day, the participant will be fit and dispensed Proclear 1 Day lenses to be worn for at least 7 days. After experiencing Proclear 1 Day lenses for at least 7 days, the participant will return for baseline variables to be evaluated and will be then be dispensed with Clariti 1 Day. The participant will be asked to return for evaluation after 7 days of lens wear. Participants will exit the study following the final evaluation of Clariti 1 Day.

[figure not shown]

Figure 1 Study flow chart (C1D = Clariti 1 Day; P1D = Proclear 1D). * Visit 1A applicable only if habitual Proclear 1 Day wearers require a change in lens power OR if participant is a habitual lens wearer of other types (see Section 4.4 for further details)

4.1.2 RANDOMIZATION

There is no randomization in this study. All participants will be habitual (or adapted) Proclear 1 Day lens wearers that will be switched into Clariti 1 Day lenses.

4.1.3 MASKING

Due to the design of the study, there is no masking of participants or investigators.

4.2 STUDY POPULATION

4.2.1 SAMPLE SIZE CALCULATION

A sample size calculation was provided by CooperVision based on the combined data for comfort scores in the BEETHOVEN 2 study (CooperVision EX-MKTG-61, data on file). For an alpha level of 0.05 and power of 0.8, a sample size of 67 participants will detect a difference of 7 units on a 0-100 scale. Seven units is accepted as a minimum meaningful difference in comfort between lenses for this scale range.²

4.2.2 NUMBER OF PARTICIPANTS

Participants will be recruited using CCLR records and advertising approved by the UW Office of Research Ethics (Appendices 25, 26, 27). Up to 75 participants will be dispensed with study

products, with a target of 67 completing the study. Informed consent will be obtained for all participants prior to their enrolment in the study (Appendix 1).

4.2.3 INCLUSION AND EXCLUSION CRITERIA

A person is eligible for inclusion in the study if he/she:

1. Is at least 17 years of age and has full legal capacity to volunteer;
2. Has read and signed an information consent letter;
3. Is willing and able to follow instructions and maintain the appointment schedule;
4. Habitually wears soft spherical contact lenses with a power between +6.00 to -10.00D (inclusive) for a minimum 5 days per week, 10 hours per day **and** anticipates no difficulty wearing contact lenses for 7 days per week, 10 hours per day;
5. Habitually wears, or is able to be adequately refit into Proclear 1 Day lenses;
6. Demonstrates an acceptable fit with Proclear 1 Day and Clariti 1 Day contact lenses;
7. Is correctable to a visual acuity of 0.20 LogMAR (approximately 20/30) or better (in each eye) with the study lenses or habitual correction;
8. Manifest cylindrical spectacle refraction does not exceed -1.00DC in either eye.

A person will be excluded from the study if he/she:

1. Is participating in any concurrent clinical research study;
2. Has any known active* ocular disease and/or infection;
3. Has a systemic condition that in the opinion of the investigator may affect a study measure;
4. Is using any systemic or topical medications that in the opinion of the investigator may affect a study measure;
5. Has known sensitivity to the diagnostic pharmaceuticals to be used in the study;
6. Is pregnant, lactating or planning a pregnancy at the time of enrolment (by verbal communication);
7. Is aphakic;
8. Has undergone refractive error surgery;
9. Is an employee of the Centre for Contact Lens Research;
10. Has taken part in another clinical or (pharmaceutical) research study within the last 7 days.

* For the purposes of this study, active ocular disease is defined as infection or inflammation which requires therapeutic treatment. Mild (i.e. not considered clinically relevant) lid abnormalities (blepharitis, meibomian gland dysfunction, papillae), corneal and conjunctival staining and dry eye are not considered active ocular disease. Neovascularization and corneal scars are the result of previous hypoxia, infection or inflammation and are therefore not active.

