4.3 STUDY MATERIALS

4.3.1 LENSES

All participants will have worn, or be fit with an optimized prescription of Proclear 1 Day for at least 7 days prior to being fit and dispensed with Clariti 1 Day. Details of both lens types used in this study are listed in Table 1.

Table 1: Lens characteristics

Lens	Clariti 1 Day (Coopervision, Inc.)	Proclear 1 Day (Coopervision, Inc.)
Material	Somofilcon A	Omafilcon A
HC licence #	81009	60845
Water content (%)	56	60
Dk/t (barrer/cm)	86	36.6
Sphere power (D)	+6.00 to -10.00D	+8.00 to - 12.00
Base curve (mm)	8.6	8.7
Diameter	14.1	14.2

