- Subjective sphero-cylindrical and best-vision sphere refraction plus distance visual acuity (high contrast, high illumination), monocular and binocular
- An ocular health assessment will be conducted
- The participant will be fit with Clariti 1 Day
- Investigator refit ratings
- Eligibility will be confirmed and the participant continues to Visit 1A

Habitual wearers of other lenses:

Participants that habitually wear other soft lens types will be asked to attend Visit 1 wearing their glasses. Participant demographics, including their contact lens history, wear schedule, health and medication will be recorded. The following procedures will then be conducted:

- Visual acuity with habitual spectacles (high contrast, high illumination)
- Automated refraction and keratometry
- Subjective sphero-cylindrical and best-vision sphere refraction plus distance visual acuity (high contrast, high illumination), monocular and binocular
- Ocular health assessment
- The participant will be fit with Clariti 1 Day
- Investigator refit ratings
- Eligibility will be confirmed and the participant continues to Visit 1A

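### The eligibility criteria do not exclude people who already wear Clariti 1 Day; if any enrol, their 'refit' is a return to their own lens and can tilt the results towards Clariti

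*Combined protocol and SAP*

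**What the plan says.** Section 2 sets the question: can habitual or adapted Proclear 1 Day wearers be refit into Clariti 1 Day and succeed after a week? The primary outcomes are the investigator's answers to the refit questions and lens fit.

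The Introduction makes habitual Proclear wearers the primary target and adds a second stream, in which "habitual wearers of other lens types will be recruited and will be adapted to Proclear 1 Day lenses for at least 7 days" before moving to Clariti. Every description of that stream is negative. Section 4.1.1 routes people to it "In the instance where the participant habitually wears lenses which are not Proclear 1 Day", and section 4.4.1.1 says "Participants that habitually wear other soft lens types will be asked to attend Visit 1 wearing their glasses".

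Three criteria in section 4.2.3 bear on the lens. Inclusion 4 asks for habitual soft spherical lenses from +6.00 to -10.00 D and names no brand. Inclusion 5 is met by a person who "Habitually wears, or is able to be adequately refit into Proclear 1 Day lenses". Inclusion 6 is met by a person who "Demonstrates an acceptable fit with Proclear 1 Day and Clariti 1 Day contact lenses". No exclusion concerns the habitual brand.

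Section 11.1 analyses all participants together. It contains no stratum, subgroup or sensitivity analysis by habitual lens.

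**The concern.** A habitual Clariti 1 Day wearer satisfies the description of the second stream. The site would give that person Proclear for at least 7 days and then dispense the lens they already wear. Inclusion 4 requires wear on at least 5 days a week for 10 hours a day, so this person has already shown that they tolerate Clariti. Proclear is the newly introduced lens, which reverses the comparison the trial wants.

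The participant adds a record to the analysis but no information about the objective. The expected direction of error is towards Clariti for the refit ratings, one-week success, the paired subjective ratings and preference. The study is open label, and lens history is recorded at Visit 1 before the refit rating is made. An investigator may therefore know that the person already wears Clariti when judging the refit.

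**Working it through.** **Could a Clariti wearer enter?** Take each rule in turn.

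- Inclusion 4: the power range, +6.00 to -10.00 D, is the same as the Clariti range in Table 1 (section 4.3.1), so no Clariti wearer in spherical lenses fails on power.
- Inclusion 5: met if Proclear can be fitted adequately.
- Inclusion 6: the Clariti half would be expected to be met; the Proclear half is settled at fitting.
- Exclusions 1 to 10: none refers to brand.
- Sections 4.4.1.1 to 4.4.1.3: as a wearer of another soft lens, the person goes through Visits 1, 1A and 1B, then to Clariti at Visit 2.

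So the rules admit this person.

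**The plan's own figure.** Section 4.2.1 gives 67 participants for a 7-unit difference (alpha 0.05, power 0.8) but no standard deviation, so it cannot be reproduced independently. Solving the paired two-sided formula n = (SD × (1.960 + 0.842) / 7)² for n = 67 gives SD ≈ 20.5. Nothing below depends on this; only n = 67 is carried forward.

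**How far could preference move?** Assumptions, none of them from the documents: k of the 67 completers are habitual Clariti wearers who choose Clariti with probability p = 0.8 to 0.9; the other 67 − k have no true preference (0.5). Section 11.1 sets 5% without stating sidedness; I take a two-sided exact binomial test.

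1. Critical count: 2 × P(Bin(67, 0.5) ≥ 42) = 0.0498, and ≥ 41 gives 0.086. The test favours Clariti from 42 of 67.
2. Expected Clariti share: (0.5(67 − k) + pk) / 67. With p = 0.9, k = 7 gives 36.3/67 = 54.2% and k = 13 gives 38.7/67 = 57.8%.
3. Chance of a false 'Clariti preferred' result: P(X + Y ≥ 42), with X ~ Bin(67 − k, 0.5) and Y ~ Bin(k, p).
4. The same with 20% of all participants answering 'no preference' (assumed), half credited to each lens as in section 11.1. The ranges cover p = 0.8 to 0.9 and half counts rounded either way.

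| Clariti wearers, k | Everyone chooses a lens | 20% 'no preference', split evenly |
|---|---|---|
| 0 | 2.5% | 1.2–1.7% |
| 3 | 4.0–4.5% | 1.9–3.0% |
| 7 | 7.0–9.4% | 3.4–6.1% |
| 13 | 14.9–23.3% | 7–15% |

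The even split lowers the level of error but leaves the relative inflation much the same. With k = 7 it is 7.0/2.5 = 2.8 to 9.4/2.5 = 3.8 times in the first column, and 3.4/1.2 = 2.8 to 6.1/1.7 = 3.6 times in the second.

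**Paired ratings.** If Clariti wearers rated their own lens 7 units higher (assumed), the pooled mean difference would shift by 7 × 7/67 = 0.7 units with 7 of them, or 7 × 13/67 = 1.4 with 13.

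**The case against.** The strongest reply is that the harm depends on recruitment. The bias needs such wearers to enrol, and the documents give no share. Habitual Proclear wearers are the primary target and Clariti is one brand within the secondary stream, so 13 of 67 would be a lot. This stands, and small counts do little: 3 such wearers move 2.5% only to 4.0–4.5%.

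Second, a reader might infer that the percentages describe a primary outcome. They do not. The primary outcomes are refit responses and lens fit, and preference is not listed as primary in the readable text. The refit items are redacted, and a 50% starting point has no basis for them, so no effect on a primary outcome can be calculated.

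Third, a reader might infer that acceptable Clariti fit is assured by admitting these people. Inclusion 6 requires it of every participant, and section 4.1.1 has everyone fitted with Clariti at screening, so the extra effect on fit acceptance is small.

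Fourth, reversed adaptation cannot explain the refit rating shown in section 4.4.1.1. For wearers of other lenses it is made at Visit 1, before their week in Proclear. What remains for that rating is the unmasked investigator's knowledge of lens history.

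Finally, the site may screen by brand in practice. Section 4.2.4 mentions current brands among the information needed for eligibility, section 4.1.2 describes everyone as being switched, and the screening form is not available to read. An operational check cannot be ruled out, but no criterion in section 4.2.3 would support it, and the brand is needed anyway to route people between the two streams.

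**Conclusion.** The gap is real: as written, section 4.2.3 lets habitual Clariti 1 Day wearers in, and section 11.1 pools them with true switchers. They cannot help answer the objective. If any enrol, they can bias the refit ratings, one-week success, paired ratings and preference towards Clariti.

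The size is unknown. Under the stated assumptions, 7 such wearers among 67 would raise the chance of a false preference finding from 2.5% to 7–9%, or from 1.2–1.7% to 3.4–6.1% if a fifth answer 'no preference'. The direction rests only on these wearers preferring Clariti more often than not.

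The documents do not support saying that the trial is biased, that such wearers were recruited, or that a primary outcome is distorted by a known amount. This is an eligibility gap worth closing because closing it is nearly free.

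**What to change.** Add an exclusion to section 4.2.3: 'Currently wears Clariti 1 Day (somofilcon A) as the habitual lens.' Contact lens history is already taken at Visit 1 (section 4.5.1), so the check needs no new procedure, only a line in the criteria and on the screening form. The cost is a slightly narrower pool in the secondary stream.

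If any such participant is already enrolled, keep them in the main analysis. They met the criteria in force, and removing them afterwards in an unmasked study would be post hoc selection. Add to section 11.1 a sensitivity analysis of refit, fit and preference without them, and report results by habitual lens.
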